## **4 STATISTICAL/ANALYTICAL ISSUES**

### **4.1 Adjustments for covariates**

No statistical testing is planned; therefore, this section is not applicable for this study.

### **4.2 Handling of dropouts or missing data**

No imputation of missing values is planned unless otherwise noted. Imputations for missing or partial dates for AEs and concomitant medications will be applied to determine if an event/medication is to be considered treatment-emergent or concomitant. Such imputations will only be performed for classifications and calculations; in the listings all data will be shown as recorded on the eCRF. Across PK, only reported data will be used.

#### **4.2.1 General imputation rule for incomplete dates**

Where necessary for the calculation of derived variables, partial dates will be completed using the earliest calendar date based on the partial date provided. This rule is valid for all partial dates with the exception of the following:

- Date of birth (DOB)
- Start and stop dates of concomitant medication
- Start and stop date of adverse events
- Start and stop dates of study medication
- Date of epilepsy diagnosis

Completely missing dates will not be replaced and the corresponding derived variables will be set to missing.

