### 2.3 Study design and conduct

EP0065 is a Phase 2 multicenter, open-label study to evaluate the PK, safety, and tolerability of iv BRV administered as a 15-minute iv infusion and an iv bolus (up to 2-minute infusion) in subjects  $\geq 1$  month to  $< 16$  years of age with epilepsy.

Study medication is defined by iv infusion of BRV administered as a 15-minute iv infusion or an iv bolus (up to 2-minute infusion). Oral BRV can be administered during EP0065 but will not be considered as study medication for EP0065.

Approximately 50 enrolled subjects will receive iv BRV in the following age-based cohorts (approximately 12 subjects/cohort):

- Cohort 1:  $\geq 12$  to  $< 16$  years
- Cohort 2:  $\geq 6$  years to  $< 12$  years
- Cohort 3:  $\geq 2$  to  $< 6$  years
- Cohort 4:  $\geq 1$  month to  $< 2$  years

The age at Screening Visit will be the determining factor for age cohort assignment. Each age cohort will have approximately 50% of subjects with iv BRV infusion and 50% with bolus BRV.

The following subjects will be eligible for enrollment in EP0065:

- Open-label BRV (OLB) subjects: currently receiving oral BRV as participants in a long-term, open-label study
- Prescribed BRV (RxB) subjects: currently receiving prescribed oral BRV from commercial supply
- Initiating Oral BRV (IOB) subjects: not currently receiving BRV; first dose of BRV in EP0065 will be oral tablet or solution
- Initiating iv BRV (IIB) subjects: not currently receiving BRV; first dose of BRV in EP0065 will be by iv Infusion

For OLB and RxB subjects, the maximum BRV dose is 5mg/kg/day (rounded). For IOB and IIB subjects, the maximum BRV dose is 4mg/kg/day. Throughout the study, no subject may receive a dose greater than BRV 200mg/day. Subjects will receive oral BRV (tablets or oral solution) in equally divided doses; BRV oral solution may be given by enteric administration (eg, by feeding tube) based on subject need.

The EP0065 study periods and visits are described below. The PK assessments will be made during the iv PK Period only and safety data will be collected throughout the study, with intensive collection of safety data with each iv BRV dose administered. A Schedule of Study Assessments is provided in the protocol for the Screening through iv PK Periods and for the Down-Titration Period and Safety (BRV-free) Periods (for subjects not continuing BRV).

- Screening Period (1 to 10 days)

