### 3.2.5 Analysis periods

This study consists of a Screening Period, an IOB Treatment Period, an iv PK Period, a Follow-up Period and a Safety (BRV-free) Period, see [Section 2.3](#) for more details on these periods.

Start of Screening Period is defined as the date of enrollment and end of Screening Period is defined as immediately before first allocated BRV treatment.

Start of IOB Treatment Period is defined as the date of first allocated oral BRV treatment and end of IOB Treatment Period is defined as immediately before first iv BRV treatment.

Start of iv PK Period is defined as the date and time of first allocated iv BRV treatment and end of iv PK Period is defined as 12 hours after start of last iv BRV treatment.

Start of Follow-up Period is defined as 12 hours after start of last iv BRV treatment and end of Follow-up Period is defined for the following scenarios:

- Subjects who transition study: as TC-1
- Subjects who do not transition and do not down-titrate: as end of study
- Subjects who down-titrate: as 12 hours after start of last down-titration treatment.

Only subjects who down-titrate have a Safety (BRV-free) Period. Start of Safety Period is defined as immediately after the end of Follow-up Period (>12 hours after start of last down-titration treatment) and end is defined as end of study.

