### 3.2.6 Exposure duration

In EP0065 study medication is defined as iv BRV.

The date and time of first study medication is defined as the start of first iv BRV infusion date and time according to the standard CRF page. The date and time of last study medication is defined as the start of last iv BRV infusion reported on the standard trial termination eCRF.

Days with unknown or zero dosing for the respective BRV formulation (iv, tablet, oral solution, oral, all) which occur between the start and end date of the respective BRV formulation will be included in the exposure calculation. For example, a day with missing or zero dosing between the first and last iv BRV dose will be included in the iv BRV exposure duration (days) and iv BRV exposure duration (hours) calculation.

The iv BRV exposure duration will be calculated separately in hours and days. Duration of iv BRV exposure in days will be calculated using the following formula:

$$\begin{aligned} &\text{iv BRV exposure duration (days)} \\ &= \text{start date and time of the last iv BRV} \\ &\quad - \text{start date and time of the first iv BRV} + 1 \text{ day} \end{aligned}$$

Duration of iv BRV exposure in hours will be calculated using the following formula:

$$\begin{aligned} &\text{iv BRV exposure duration (hours)} \\ &= \text{start date and time of the last iv BRV} \\ &\quad - \text{start date and time of the first iv BRV} + 1 \text{ hour} \end{aligned}$$

The duration of oral BRV exposure will be calculated in days only by administration method (tablets or oral solution) and over both administration methods separately for the IOB Treatment Period and Follow-up Period. The duration of oral BRV will be calculated separately for each period using the following formulas:

$$\begin{aligned} &\text{Oral BRV exposure duration from tablets during period (days)} \\ &= \text{end date of last BRV tablet during period} \\ &\quad - \text{start date of first BRV tablet during period} + 1 \text{ day} \end{aligned}$$

$$\begin{aligned} &\text{Oral BRV exposure duration from oral solution during period (days)} \\ &= \text{end date of last oral solution BRV during period} \\ &\quad - \text{start date of first oral solution BRV during period} + 1 \text{ day} \end{aligned}$$

$$\begin{aligned} &\text{Overall Oral BRV exposure duration during period (days)} \\ &= \text{end date of last oral BRV during period} \\ &\quad - \text{start date of first oral BRV during period} + 1 \text{ day} \end{aligned}$$

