#### 4.2.5 Handling of study medication with partial or missing date

No imputation should be performed for missing study medication start dates. This field on the eCRF should not be partial or missing.

For partial or missing date of last dose of study medication, the following imputation rules will be applied for the purpose of calculating overall exposure:

- If the day is missing (but month and year available), impute the last dose date as the earliest of the last day of the month or the date of last contact reported on the trial termination eCRF; if day and month are both missing (only year available), impute the last dose date as the earliest of the last day of the year or the date of last contact on the trial termination eCRF.
- If a subject died and has a partial or missing last dose date, the last dose date is to be set to the date of death. If there is a partial date of last dose and the month/year are prior to the month and year of the date of death, follow partial date imputation rules.
- If the last dose date is completely missing and no information could be obtained from data cleaning exercises, the last dose date should be imputed as the date of last contact according to the study termination eCRF. A review of the data for subjects with completely missing last dose dates should be performed to ensure that the imputation does not result in an unrealistic value for duration of exposure.

Imputed date of last dose dates should only be used for calculation of the duration of exposure. The date as recorded on the eCRF should be presented in subject data listings (no imputed dates should be included in subject data listings).

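### A partial oral BRV stop date falls under the SAP's earliest-date rule, which can shorten or invert oral exposure and nearly always starts the BRV-free Safety Period too early after an oral taper

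*SAP*

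**What the plan says.** - **General rule.** Under SAP 4.2.1, "partial dates will be completed using the earliest calendar date based on the partial date provided". Five types of date are excepted. The only one that could cover oral BRV is "Start and stop dates of study medication".
- **What study medication means.** SAP 2.3: "Oral BRV can be administered during EP0065 but will not be considered as study medication for EP0065". SAP 3.2.6 repeats it: "In EP0065 study medication is defined as iv BRV".
- **Last-dose rule.** SAP 4.2.5 completes a partial last-dose date of study medication late: the earlier of the end of the month (or year) and the date of last contact.
- **Oral exposure.** SAP 3.2.6 derives it separately for the IOB Treatment and Follow-up Periods. It takes the "end date of last oral BRV during period", subtracts the first date and adds one day. Overall BRV exposure ends at the latest BRV date of either route.
- **Period boundary.** SAP 3.2.5 ends the Follow-up Period thus: "Subjects who down-titrate: as 12 hours after start of last down-titration treatment". The Safety Period begins straight after. SAP 10.2.1 assigns each adverse event to the period in which it began, and SAP 5.1 uses the last down-titration dose to count subjects starting the Safety Period.

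**The concern.** The SAP has no separate rule for oral BRV dates, so they fall to the general rule, and for a stop date the earliest possible date errs in one direction only. The SAP avoids this elsewhere. Partial stop dates of concomitant medication (4.2.3) and adverse events (4.2.4) go to the end of the month or year, and the last iv dose goes late under 4.2.5. Oral BRV is the one treatment stop date left on the opposite rule, apparently as a by-product of defining study medication as iv only.

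At stake are oral exposure, overall BRV exposure, the boundary between Follow-up and Safety Periods, the by-period adverse event tables on the Safety Set, and the Safety Period disposition count. The boundary matters most, because it separates events on tapering BRV from events off BRV.

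**Working it through.** The plan states no figure for this point, so the check applies its rules by calendar arithmetic.

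**Inputs.** Down-titration lasts at most 4 weeks (SAP 2.3), so the true oral duration L is at most 28 days. The IOB Treatment Period lasts 2 to 10 days. Exposure = stop − start + 1 (SAP 3.2.6).

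**Assumptions.** The first oral dose of the period is fully known and equally likely on each day of a 365-day year. The stop date has month and year but no day.

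**Exposure.** The imputed stop is the 1st of the stop month. If start (day s) and stop share a month, imputed duration = 1 − s + 1 = 2 − s, which is zero or negative when s ≥ 2. In a month of n days this holds for s = 2 to n − L + 1, that is n − L start days. Over twelve months that is 365 − 12L. The result is exact only if the true stop was the 1st (12 start days). The other 12(L − 1) start days give a positive but shortened duration.

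| L (days) | Zero or negative | Positive but too short | Exact |
|---|---|---|---|
| 7 | 281/365 = 77.0% | 72/365 = 19.7% | 3.3% |
| 14 | 197/365 = 54.0% | 156/365 = 42.7% | 3.3% |
| 21 | 113/365 = 31.0% | 240/365 = 65.8% | 3.3% |
| 28 | 29/365 = 7.9% | 324/365 = 88.8% | 3.3% |

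If the month is missing too, zero or negative occurs in 92.3% of cases at 28 days.

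Examples:
- 7 to 28 June, true 22 days: 1 − 7 + 1 = −5.
- 20 June to 17 July, true 28 days: imputed stop 1 July, giving 12.

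Overall BRV exposure uses the latest date of either route. With complete iv dates it is shortened, but not below the last iv dose. It can reach zero or less only in a subject with oral doses alone.

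**Safety Period start.** With the true last taper dose on day D of the month, the period starts D − 1 days early.
- It is early unless D = 1: 353/365 = 96.7%.
- The mean is (7 × 465 + 4 × 435 + 378)/365 = 5373/365 = 14.7 days, and the maximum is 30.
- The table also locates the imputed stop. The zero-or-negative column is the share falling before the first taper dose; the next column is the share falling inside the taper.

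In the two examples the Safety Period starts 27 and 16 days early.

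**Check of a late rule.** Take the earlier of month-end and last contact, with last contact assumed 14 days after the last dose. No duration is then zero or negative, and the result lies between L and L + 14 days (28 to 42 for a 28-day taper). For 7 to 28 June it gives 24 days against a true 22.

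**The case against.** **Another reading of 4.2.5 exists.** That section introduces its rule with: "For partial or missing date of last dose of study medication, the following imputation rules will be applied for the purpose of calculating overall exposure". SAP 3.2.6 uses the overall label for oral plus iv BRV, so a programmer could apply 4.2.5 to oral dates. This is a fair reading for exposure, although SAP 10.1 refers to 4.2.5 only in its iv paragraph. It does not rescue the period boundary, because 4.2.5 adds: "Imputed date of last dose dates should only be used for calculation of the duration of exposure".

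**Partial oral stop dates may be rare.** A reader might infer that home dosing makes them common. The documents do not say so, and several procedures work against it. In the IOB Treatment Period the first iv dose is timed about 12 hours after the prior oral dose (protocol 5.1), so a site following the protocol knows that date. For tapers, accountability is done with the subject present (protocol 7.7), oral BRV is collected at Visit 13 (8.6), and TC-3 is scheduled from the final dose (8.7). This objection stands: the percentages describe what happens given a partial date, not how often one occurs.

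**The reach is limited.** A reader might infer that the rule always gives zero or negative exposure, or that it disturbs the main safety tables. Neither is supported. A full 28-day taper with only the day missing is usually shortened. Treatment-emergent status depends on the first BRV (SAP 10.2), and the main adverse event tables combine all periods (10.2.1). The IOB Treatment Period ends at the first iv dose (3.2.5), so no event moves there. Iv tapers are study medication and fall outside 4.2.1's rule. Completely missing dates are left missing.

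**Conclusion.** The point holds in a limited form. Read literally, the SAP completes a partial oral BRV stop date with the earliest date. For a subject with such a date:

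- Oral exposure can be shortened, zero or negative, and overall BRV exposure shortened. Which error dominates depends on the length of the course.
- After an oral taper the Safety Period nearly always starts too early. Events that begin during the taper can then appear as Safety Period events in the by-period tables, and the disposition count can be affected.

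The sizes rest on a known start date, uniform start days and a missing day only. The affected outputs are descriptive, in a study of about 50 subjects with no hypothesis tests. This is a minor defect, worth correcting because the remedy is cheap and the present text permits two readings with different results.

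**What to change.** 1. In SAP 4.2.1, add start and stop dates of oral BRV to the exceptions. State in 4.2.5 whether its no-imputation rule for start dates then covers oral BRV.
2. In SAP 4.2.5, extend the rule for partial last-dose dates to oral BRV: the earlier of the end of the month (or year) and a known bound. The bound is the first iv BRV for the IOB Treatment Period, and Visit 13 or last contact for down-titration. The imputed date is never before the first oral dose of that period.
3. Amend the 4.2.5 sentence that confines imputed last-dose dates to exposure duration, so that the same bounded date also sets the end of Follow-up and the start of the Safety Period. Without this, step 2 repairs exposure only.

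The cost is a few sentences and a few lines of code, with no new data. The downside is that a late rule can modestly overstate exposure, by up to 14 days under the last-contact assumption above, and can place events from just after the taper in Follow-up. Bounding by Visit 13 where available limits both.

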#### 4.2.3 Handling of prior and concomitant medications with partial or missing date

Any medications with incomplete start and end dates will be handled according to the following rules for classification as prior and concomitant and for the calculation of relative study days. Such imputations will only be performed for these classifications and calculations; in the listings all data will be shown as recorded on the eCRF.

##### Imputation of Partial Start Dates

- If only the month and year are specified and the month and year of first dose of iv BRV is not the same as the month and year of the start date, then use the 1st of the month.
- If only the month and year are specified and the month and year of first dose of iv BRV is the same as the month and year of the start, then use the date of first dose of iv BRV.
- If only the year is specified, and the year of first dose of iv BRV is not the same as the year of the start date, then use 1 Jan of the year of the start date.
- If only the year is specified, and the year of first dose of iv BRV is the same as the year of the start date, then use the date of first dose of iv BRV.
- If the start date is completely unknown and the stop date is unknown or not prior to the date of first dose of iv BRV, then use the date of first dose of iv BRV.

##### Imputation of Partial Stop Dates

- If only the month and year are specified, then use the last day of the month.
- If only the year is specified, then use 31 Dec of that year.
- If the stop date is completely unknown, do not impute the stop date.

In the event of ambiguity or incomplete data which makes it impossible to determine whether a medication was concomitant or not, the medication will be considered as concomitant.

#### 4.2.4 Handling of adverse events with partial or missing date

Any AEs with incomplete onset and outcome (end) dates/times will be handled according to the following rules for classification as treatment-emergent. Such imputations will only be performed for these classifications; in the listings all data will be shown as recorded on the eCRF.

### Imputation of Partial AE Onset Dates

- If only the month and year are specified and the month and year of first dose of iv BRV or oral BRV from IOB Treatment Period is not the same as the month and year of AE onset, then use the 1st of the month of onset.
- If only the month and year are specified and the month and year of first dose of iv BRV is the same as the month and year of AE onset, then use the date/time of first dose of iv BRV.
- If only the month and year are specified and the month and year of first dose of iv BRV is not the same as the month and year of AE onset, but the month and year of first dose of oral BRV during the IOB Treatment Period is the same then use the date/time of first dose of oral BRV.
- If only the year is specified, and the year of first dose of iv BRV or oral BRV from IOB Treatment Period is not the same as the year of AE onset, then use 1 Jan of the year of onset.
- If only the year is specified, and the year of first dose of iv BRV is the same as the year of AE onset, then use the date/time of first dose of iv BRV.
- If only the year is specified and the year of first dose of iv BRV is not the same as the year of AE onset, but the year of first dose of oral BRV during the IOB Treatment Period is the same then use the date/time of first dose of oral BRV.
- If the AE onset date is completely unknown, then use the date/time of first dose of iv BRV.
- If the AE onset time of the event is unknown, impute it as 00:00 unless the known part of the AE onset date is the same as the date of first iv BRV dose; in this case impute the time of first dose of iv BRV dose.

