6 SELECTION AND WITHDRAWAL OF SUBJECTS

6.1 Inclusion criteria

To be eligible to participate in this study, all of the following criteria must be met:

1. Subject or the parent(s) or legal representative of the subject has signed and dated an Institutional Review Board (IRB)/Independent Ethics Committee (IEC) approved written ICF. The ICF or a specific Assent form, where required, will be signed and dated by minors.
2. The Investigator considers the subject/legal representative to be reliable and able to comply with all study requirements.
3. Subject is male or female from ≥ 1 month to <16 years of age. For subjects who are <1 year from birth and who were preterm infants, the corrected gestational age should be used for this entry requirement. The corrected gestational age is calculated by subtracting the number of weeks born before 37 weeks of gestation from the chronological age.
4. Subject weighs ≥ 3 kg (6.6lbs).
5. Subject has a diagnosis of epilepsy.
6. Subject is an acceptable candidate for venipuncture and iv infusion.
7. Subject being treated with ≥ 1 AED (including BRV) without a change of dose regimen for at least 7 days prior to Screening.
8. Subject is not being treated with vagus nerve stimulation (VNS), OR the subject is being treated with VNS and the settings have been constant for ≥ 7 days prior to Screening.
9. For female subjects, the subject is
 - Not of childbearing potential
 - OR-
 - Of childbearing potential, and
 - Is not sexually active
 - Has a negative pregnancy test
 - OR-
 - Of childbearing potential, and
 - Is sexually active
 - Has a negative pregnancy test

- Understands the consequences and potential risks of inadequately protected sexual activity, understands and properly uses contraceptive methods, and is willing to inform the Investigator of any contraception changes. Medically acceptable contraceptive methods for the study include, but are not limited to:
 - Oral or depot contraceptive treatment with at least ethinylestradiol 30µg per intake or ethinylestradiol 50µg per intake if also taking one of the following: carbamazepine, phenobarbital, primidone, phenytoin, oxcarbazepine, St. John's Wort, or rifampicin.
 - Barrier contraception: Intra Uterine Device, diaphragm with spermicide, male or female condom with spermicide
 - Abstinence from sexual intercourse

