### **6.3 Prior and concomitant medications**

Prior medications include any medications that started prior to the date of first dose of iv BRV. Only prior medication which is ongoing or has an end date in the 2 weeks prior to screening will be included in summaries. Prior medication with an end date prior to the 2 weeks before screening will be listed only. Concomitant medications are medications taken on at least one day in common with the iv PK Treatment Period. Medications may be both prior and concomitant. Medications which started after the day of the last iv BRV treatment will be categorized as follow-up medications.

For OLB subjects only medication which started during the EP0065 study will be recorded in the EP0065 study. Information of medication which started before EP0065 study start will come from the respective OLB study. Only medications with a stop date  $\leq$  14 days prior to start date of EP0065 will be summarized in EP0065.

Antiepileptic drugs (AED) will be identified using an internal UCB AED list (file: AEDs\_ATCs\_SEP2017\_FINAL\_benzo\_groups\_23JUL2019.xls).

Subject data listings for prior, concomitant and follow-up AEDs, and prior, concomitant and follow-up non-AEDs will be provided separately together with a listing of medication glossary including all reported medications.

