## 10.2 Adverse Events

All adverse events (AEs) occurring during EP0065 (ie, after signing of the ICF) must be reported. For subjects who transition to study N01266, any AEs which began after the first dose of BRV in N01266 but prior to TC-1 of EP0065 will be considered as during EP0065 and N01266. Pre-treatment adverse events (PTAEs) are defined as AEs that had onset strictly prior to the date/time of the first BRV medication taken during EP0065. For OLB subjects, where the AE started prior to EP0065 enrollment, information will come from the respective OLB study.

Treatment-emergent adverse events (TEAEs) are defined as those events which started on or after the first BRV medication taken during the EP0065 study. Subjects who began the study on BRV treatment (OLB and RxB subjects) will be assumed to have taken BRV treatment on the first day of screening. Timing of an AE being treatment emergent varies by subject group: all AEs are treatment emergent for RxB and OLB subjects; all AEs on or after the IOB Treatment Period are treatment emergent for IOB subjects; all AEs on or after the iv PK Period are treatment emergent for IIB subjects.

Data handling rules for management of missing or partial start or stop dates for adverse events should follow those defined in the [Section 4.2.4](#). The classification of TEAE will be done after imputation of any partial start dates.

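### The partial-date rules for AE onsets and medication starts do not check the recorded end date, so some events and drugs that ended before the first infusion are given a start after they ended and are misclassified

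*SAP*

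**What the plan says.** **AE onsets.** For a month-only onset, SAP 4.2.4 (Imputation of Partial AE Onset Dates) reads: "month and year of first dose of iv BRV is the same as the month and year of AE onset, then use the date/time", that is, the first infusion. A year-only onset in the year of the first infusion is handled in the same way. For no date at all: "If the AE onset date is completely unknown, then use the date/time of first dose of iv BRV". If only an IOB child's first oral dose falls in the onset month or year, that oral dose is used. No bullet refers to the event's end date. SAP 10.2 fixes the order of work: "The classification of TEAE will be done after imputation of any partial start dates".

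**Medication starts.** SAP 4.2.3 (Imputation of Partial Start Dates) follows the same pattern for month-only starts and for year-only starts: "If only the year is specified, and the year of first dose of iv BRV is the same as the year of the start date", the first iv date is used. Only the bullet for a wholly missing start looks at the stop date: "If the start date is completely unknown and the stop date is unknown or not prior to the date of first dose of iv BRV". SAP 6.3 then states: "Prior medications include any medications that started prior to the date of first dose of iv BRV". A concomitant medication must share at least one day with the iv PK Period.

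**Last iv dose.** SAP 3.2.6 takes the last infusion from the trial termination page. If its day is missing, SAP 4.2.5 says to "impute the last dose date as the earliest of the last day of the month or the date of last contact". Protocol 7.7 has site staff record the date and time of every infusion.

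**The concern.** A recorded end date is an upper bound on the start. If it falls before the first dose, pre-treatment status is known whatever part of the onset date is missing. The rules override that bound and can produce a start later than the end.

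AEs are a primary safety variable, and cells are small: about 12 children per cohort, half per infusion duration. One pre-treatment event moved into the treatment-emergent (TEAE) tables is visible in such a cell.

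On the medication side the gap is not conservative, because true background therapy is dropped from the prior summaries. The guard is also placed oddly: a drug with a known start month is less protected than one with no start date. The youngest cohort is the most exposed, since for a child born in the infusion year every year-only start triggers the rule.

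**Working it through.** The plan gives no figure to reproduce. The check traces the bullets literally with example dates.

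**1. IIB adverse event.** Onset June 2019, end 5 June, first infusion 10 June. The month matches, so the imputed onset is 10 June: 10 − 5 = 5 days after the event ended. Under SAP 10.2 the IIB threshold is the start of the iv PK Period, so a pre-treatment event becomes a TEAE. Year-only (2019) and unknown onsets give the same result.

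**2. IOB screening event.** Oral dosing from 3 June, first infusion 10 June, onset June, ended before 3 June. The iv month matches, so the onset becomes 10 June. That is after the oral threshold, so the event is a TEAE although it ended before any study brivaracetam.

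**3. OLB and RxB.** SAP 10.2 already counts all their AEs as treatment-emergent. Status cannot change.

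**4. Stopped drug.** Start June 2019, stop 5 June, first infusion 10 June. The imputed start is 10 June. It is not prior (start not before the first iv date), not concomitant (stopped before the iv PK Period) and not follow-up (did not start after the last iv day). It leaves every summary.

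**5. Ongoing antiepileptic drug.** Start 2019, infusion November 2019. The imputed start is infusion day, so the drug leaves the prior table and stays in the concomitant table. A start of 2015 becomes 1 January 2015 and is handled correctly. For IOB and IIB children, inclusion criterion 7 requires at least one antiepileptic drug "without a change of dose regimen for at least 7 days prior to Screening". As they are not on brivaracetam, this must be another drug, and infusion day cannot be its true start.

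**6. How often a partial pre-infusion onset is moved.** Assume onsets spread evenly over the 10 days before infusion and infusion dates spread evenly over the calendar. The mean lag is (1 + … + 10)/10 = 5.5 days.
- Month-only: share in the same month as the infusion = 1 − 5.5/30.44 = 82%.
- Year-only: 1 − 5.5/365.25 = 98.5%.
- Over a 20-day window (mean lag 10.5 days): 65.5% and 97%. For IOB children many of these onsets follow the first oral dose and are TEAEs anyway.

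These are shares of events whose onset day is missing, not of all events. A wrong status also needs a recorded end before the first dose.

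**7. Last iv dose.** SAP 3.2.6: exposure in days = last start − first start + 1.
- Two doses 12 hours apart: 0.5 + 1 = 1.5 days.
- Last dose moved to a TC-1 held 1 to 3 days later in the same month: 0.5 + 1 + 1 = 2.5, up to 0.5 + 3 + 1 = 4.5 days.
- Dosing on 3–4 June with last contact on 30 June: 30 − 3 + 1 = 28 days, against 4 − 3 + 1 = 2. Last contact is then 26 days after the last infusion, which needs follow-up well beyond TC-1, such as down-titration.

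**The case against.** The strongest reply is that calling a doubtful event treatment-emergent is deliberately conservative, and that the study is descriptive with no testing. The first part fails here. The SAP reserves that default for cases where status cannot be determined, and an end date before the first dose determines it. The second part limits the importance but does not remove the error.

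Four stronger readings are tempting and are not supported:

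- **That resolved events are attributed to iv brivaracetam.** Treatment-emergent is not drug-related. Relationship is the investigator's assessment, and TEAEs are defined from the first brivaracetam dose in the study, oral or iv. Listings show recorded dates. SAP 4.2.4 confines the imputation to TEAE classification. SAP 4.2 speaks more widely of classifications and calculations, so tables by period or by time since infusion would be affected only if imputed onsets were used there.
- **That background drugs appear newly started.** No planned summary reports start dates or new starts, and an ongoing drug stays in the concomitant table. SAP 3.2.3 also says that relative day is not calculated for partial dates, although SAP 4.2.3 reads otherwise. The actual effect is an undercount in the prior tables.
- **That inclusion criterion 7 bounds every antiepileptic drug.** It requires one, and brivaracetam counts, so OLB and RxB children may meet it with brivaracetam alone.
- **That iv exposure is materially inflated.** Infusions are supervised and timed, the rule needs an incomplete date on the termination page, and it feeds exposure duration only. A wholly missing date also gets a plausibility review; a missing day does not.

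The AE case is also narrow: Screening lasts 1 to 10 days and AEs are prompted at each visit, so an onset with no day but a full end date should be uncommon.

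**Conclusion.** The gap is real but limited. As written, SAP 4.2.4 gives impossible onset dates and turns into TEAEs some IIB events that ended before iv dosing and some IOB events that ended before oral dosing. SAP 4.2.3 removes some true prior medications from the prior summaries. The last-dose rule is a minor companion issue.

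The documents do not say how many dates are partial. They are likely few, so the expected effect is small. If one event is affected, it shifts a nominal 6-child cell by 1/6, about 17 percentage points. The conclusion rests on a literal reading of the bullets; an unwritten programming check on end dates would prevent the AE errors and the stopped-drug error.

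**What to change.** **(a) AE onset.** State that no imputed onset may be later than the recorded end date.
- If the event ended before the first brivaracetam dose in the study (oral for IOB, iv for IIB), use the earliest date consistent with the partial date, so that it is pre-treatment. For a wholly unknown onset the cap at the end date is enough.
- If an IOB event ended on or after first oral dosing but before the first infusion, use the later of the first oral dose and the earliest consistent date, so that it stays a TEAE.

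The second branch is needed. With oral dosing from 3 June, infusion on 10 June, onset June and end 8 June, a blanket move to 1 June would wrongly make a possibly treatment-emergent event pre-treatment.

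**(b) Medications.** Apply the same cap to medication starts by extending the stop-date condition to month-only and year-only starts. For medications recorded as in use at Screening, impute the earliest date consistent with the partial date.

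**(c) Last iv dose (minor).** Take it from the infusion records and use SAP 4.2.5 only if no record exists. The first iv dose already comes from the case report form's infusion data and is not imputed.

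The cost is a few SAP sentences and minor programming, with no change to data collection.
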